### **2.1.6. Exploratory Estimands**

For the exploratory objective to further describe the immune response for MenB induced by 2 doses of MenABCWY administered on a 0- and 12-month schedule, the estimand has the following attributes:

- Population: Participants receiving 2 doses of MenABCWY and who are in compliance with the key protocol criteria (evaluable participants).
- Variable: hSBA titer for each of the primary MenB test strains (A22, A56, B24, and B44).

- Intercurrent event(s): Participants will be summarized according to the vaccine group to which they were randomized. Missing serology data will not be imputed.
- Population-level summary:
  - The percentage of participants with hSBA titers  $\geq 1:4$ ,  $\geq 1:8$ ,  $\geq 1:16$ ,  $\geq 1:32$ ,  $\geq 1:64$ , and  $\geq 1:128$  for each of the 4 primary MenB test strains at baseline and 1 month after the second dose of MenABCWY in Group 1 (0- and 12-month schedule).
  - hSBA GMTs for each of the 4 primary MenB test strains at baseline and 1 month after the second dose of MenABCWY in Group 1 (0- and 12-month schedule).
  - The percentage of participants achieving an hSBA titer  $\geq$  LLOQ (1:16 for strain A22 and 1:8 for strains A56, B24, and B44) for all 4 primary MenB test strains combined (composite response) at baseline and 1 month after the second dose of MenABCWY in Group 1 (0- and 12-month schedule).
  - The percentage of participants achieving at least a 4-fold rise in hSBA titer from baseline for each of the 4 primary MenB test strains at 1 month after the second dose of MenABCWY in Group 1 (0- and 12-month schedule).
    - For participants with a baseline hSBA titer below the LOD (or an hSBA titer of  $< 1:4$ ), a 4-fold response is defined as an hSBA titer of  $\geq 1:16$ .
    - For participants with a baseline hSBA titer of  $\geq$  LOD (ie, hSBA titer of  $\geq 1:4$ ) and  $<$  LLOQ, a 4-fold response is defined as an hSBA titer of  $\geq 4$  times the LLOQ.
    - For participants with a baseline hSBA titer of  $\geq$  LLOQ, a 4-fold response is defined as an hSBA titer of  $\geq 4$  times the baseline titer.

For the exploratory objective to further describe the immune response for MenB induced by 2 doses of MenABCWY administered on a 0- and 36-month schedule, the estimand has the following attributes:

- Population: Participants receiving 2 doses of MenABCWY and who are in compliance with the key protocol criteria (evaluable participants).
- Variable: hSBA titer for each of the primary MenB test strains (A22, A56, B24, and B44).
- Intercurrent event(s): Participants will be summarized according to the vaccine group to which they were randomized. Missing serology data will not be imputed.

- Population-level summary:
  - The percentage of participants with hSBA titers  $\geq 1:4$ ,  $\geq 1:8$ ,  $\geq 1:16$ ,  $\geq 1:32$ ,  $\geq 1:64$ , and  $\geq 1:128$  for each of the 4 primary MenB test strains at baseline and 1 month after the second dose of MenABCWY in Group 2 (0- and 36-month schedule).
  - hSBA GMTs for each of the 4 primary MenB test strains at baseline, 13 months after the first dose of MenABCWY, and 1 month after the second dose of MenABCWY in Group 2 (0- and 36-month schedule).
  - The percentage of participants achieving an hSBA titer  $\geq$  LLOQ (1:16 for strain A22 and 1:8 for strains A56, B24, and B44) for all 4 primary MenB test strains combined (composite response) at baseline and 1 month after the second dose of MenABCWY in Group 2 (0- and 36-month schedule).
  - The percentage of participants achieving an hSBA titer  $\geq$  LLOQ for each of the 4 primary MenB test strains at 13 months after the first dose of MenABCWY in Group 2 (0- and 36-month schedule).
  - The percentage of participants achieving at least a 4-fold rise in hSBA titer from baseline for each of the 4 primary MenB test strains at 1 month after the second dose of MenABCWY in Group 2 (0- and 36-month schedule).
    - For participants with a baseline hSBA titer below the LOD (or an hSBA titer of  $< 1:4$ ), a 4-fold response is defined as an hSBA titer of  $\geq 1:16$ .
    - For participants with a baseline hSBA titer of  $\geq$  LOD (ie, hSBA titer of  $\geq 1:4$ ) and  $<$  LLOQ, a 4-fold response is defined as an hSBA titer of  $\geq 4$  times the LLOQ.
    - For participants with a baseline hSBA titer of  $\geq$  LLOQ, a 4-fold response is defined as an hSBA titer of  $\geq 4$  times the baseline titer.

For the exploratory objective to further describe the immune response for MenB induced by 2 doses of MenABCWY administered on both dose schedules, the endpoints related to the percentage of participants with hSBA titers  $\geq 1:8$ ,  $\geq 1:16$ ,  $\geq 1:32$ ,  $\geq 1:64$ , and  $\geq 1:128$  may not be reported. This will not extend to reporting of the primary endpoint of percentage of participants achieving hSBA titers  $\geq$  LLOQ and  $\geq 1:4$ . In addition, the endpoint related to hSBA GMTs for each of the 4 primary MenB test strains at 13 months after the first dose of MenABCWY in Group 2 will not be reported.

For the exploratory objective to further describe the immune response for MenA, MenC, MenW, and MenY induced by 1 and 2 doses of MenABCWY administered on a 0- and 12-month schedule, the estimand has the following attributes:

After 1 dose of MenABCWY:

- Population: Participants receiving 1 dose of MenABCWY and who are in compliance with the key protocol criteria (evaluable participants).
- Variable: hSBA titer for each of the ACWY test strains.
- Intercurrent event(s): Participants will be summarized according to the vaccine group to which they were randomized. Missing serology data will not be imputed.
- Population-level summary:
  - hSBA GMTs for each ACWY test strain at baseline and 1 month after the first dose of MenABCWY in Group 1 (0- and 12-month schedule).
  - The percentage of participants achieving at least a 4-fold rise in hSBA titer from baseline for each ACWY test strain at 1 month after the first dose of MenABCWY in Group 1 (0- and 12-month schedule).
    - For participants with a baseline hSBA titer below the LOD (or an hSBA titer of  $<1:4$ ), a 4-fold response is defined as an hSBA titer of  $\geq 1:16$ .
    - For participants with a baseline hSBA titer of  $\geq$  LOD (ie, hSBA titer of  $\geq 1:4$ ) and  $<$  LLOQ, a 4-fold response is defined as an hSBA titer of  $\geq 4$  times the LLOQ.
    - For participants with a baseline hSBA titer of  $\geq$  LLOQ, a 4-fold response is defined as an hSBA titer of  $\geq 4$  times the baseline titer.

After 2 doses of MenABCWY:

- Population: Participants receiving 2 doses of MenABCWY and who are in compliance with the key protocol criteria (evaluable participants).
- Variable: hSBA titer for each of the ACWY test strains.
- Intercurrent event(s): Participants will be summarized according to the vaccine group to which they were randomized. Missing serology data will not be imputed.
- Population-level summary:
  - hSBA GMTs for each ACWY test strain at baseline and 1 month after the second dose of MenABCWY in Group 1 (0- and 12-month schedule).
  - The percentage of participants achieving at least a 4-fold rise in hSBA titer from baseline for each ACWY test strain at 1 month after the second dose of MenABCWY in Group 1 (0- and 12-month schedule).

- For participants with a baseline hSBA titer below the LOD (or an hSBA titer of  $<1:4$ ), a 4-fold response is defined as an hSBA titer of  $\geq 1:16$ .
- For participants with a baseline hSBA titer of  $\geq$  LOD (ie, hSBA titer of  $\geq 1:4$ ) and  $<$  LLOQ, a 4-fold response is defined as an hSBA titer of  $\geq 4$  times the LLOQ.
- For participants with a baseline hSBA titer of  $\geq$  LLOQ, a 4-fold response is defined as an hSBA titer of  $\geq 4$  times the baseline titer.

For the exploratory objective to further describe the immune response for MenA, MenC, MenW, and MenY induced by 1 and 2 doses of MenABCWY administered on a 0- and 36-month schedule, the estimand has the following attributes:

After 1 dose of MenABCWY:

- Population: Participants receiving 1 dose of MenABCWY and who are in compliance with the key protocol criteria (evaluable participants).
- Variable: hSBA titer for each of the ACWY test strains.
- Intercurrent event(s): Participants will be summarized according to the vaccine group to which they were randomized. Missing serology data will not be imputed.
- Population-level summary:
- hSBA GMTs for each ACWY test strain at baseline, 1 month after the first dose of MenABCWY, and 13 months after the first dose of MenABCWY in Group 2 (0- and 36-month schedule).
- The percentage of participants achieving an hSBA titer  $\geq$  LLOQ for each ACWY test strain at 13 months after the first dose of MenABCWY in Group 2 (0- and 36-month schedule).
- The percentage of participants achieving at least a 4-fold rise in hSBA titer from baseline for each ACWY test strain at 1 month after the first dose of MenABCWY in Group 2 (0- and 36-month schedule).
  - For participants with a baseline hSBA titer below the LOD (or an hSBA titer of  $<1:4$ ), a 4-fold response is defined as an hSBA titer of  $\geq 1:16$ .
  - For participants with a baseline hSBA titer of  $\geq$  LOD (ie, hSBA titer of  $\geq 1:4$ ) and  $<$  LLOQ, a 4-fold response is defined as an hSBA titer of  $\geq 4$  times the LLOQ.
  - For participants with a baseline hSBA titer of  $\geq$  LLOQ, a 4-fold response is defined as an hSBA titer of  $\geq 4$  times the baseline titer.

For the exploratory objective to further describe the immune response for MenA, MenC, MenW, and MenY induced by 1 dose of MenABCWY administered on a 0- and 36-month schedule, the endpoint related to hSBA GMTs for each of the ACWY test strains at 13 months after the first dose of MenABCWY in Group 2 will not be reported.

After 2 doses of MenABCWY:

- Population: Participants receiving 2 doses of MenABCWY and who are in compliance with the key protocol criteria (evaluable participants).
- Variable: hSBA titer for each of the ACWY test strains.
- Intercurrent event(s): Participants will be summarized according to the vaccine group to which they were randomized. Missing serology data will not be imputed.
- Population-level summary:
  - hSBA GMTs for each ACWY test strain at baseline and 1 month after the second dose of MenABCWY in Group 2 (0- and 36-month schedule).
  - The percentage of participants achieving at least a 4-fold rise in hSBA titer from baseline for each ACWY test strain at 1 month after the second dose of MenABCWY in Group 2 (0- and 36-month schedule).
    - For participants with a baseline hSBA titer below the LOD (or an hSBA titer of  $<1:4$ ), a 4-fold response is defined as an hSBA titer of  $\geq 1:16$ .
    - For participants with a baseline hSBA titer of  $\geq$  LOD (ie, hSBA titer of  $\geq 1:4$ ) and  $<$  LLOQ, a 4-fold response is defined as an hSBA titer of  $\geq 4$  times the LLOQ.
    - For participants with a baseline hSBA titer of  $\geq$  LLOQ, a 4-fold response is defined as an hSBA titer of  $\geq 4$  times the baseline titer.

## 2.2. Study Design

This is a Phase 2b, randomized, observer-blinded, multicenter trial in which approximately 300 US participants  $\geq 11$  to  $<15$  years of age will be randomly assigned at a 1:1 ratio to receive MenABCWY either on a 0- and 12-month schedule (Group 1) or on a 0- and 36-month schedule (Group 2) as shown in [Table 2](#). All participants will be naïve to any meningococcal vaccine prior to enrollment.

Participants will have blood drawn prior to Vaccination 1 and 1 month after each vaccination. Additionally, to facilitate the description of antibody persistence after 2 doses of MenABCWY, participants in Group 1 (0- and 12-month schedule) will have blood drawn at 12 and 24 months after the second dose of MenABCWY. The sponsor will be blinded to dosing schedule assignment through Month 13 (1 month after the second dose of

MenABCWY in Group 1 [0- and 12-month schedule]), after which the dosing schedule assignment for all participants will be unblinded. The second dose of MenABCWY in Group 2 (0- and 36-month schedule) will be administered in an open-label manner. Each participant will participate in the study for approximately 37 months. Approximately 300 participants will be enrolled in the study.

## 2.2.1. Schedule of Activities (SoA)

The SoA table provides an overview of the protocol visits and procedures. Refer to the STUDY ASSESSMENTS AND PROCEDURES section of the protocol for detailed information on each procedure and assessment required for compliance with the protocol. The investigator may schedule visits (unplanned visits) in addition to those listed in the SoA table, in order to conduct evaluations or assessments required to protect the well-being of the participant.

Group 1 (0- and 12-Month Schedule)							
Visit Identifier	Visit 1	Visit 2	Visit 3	Visit 4	Visit 5	Visit 6	Visit 7 a
Visit Description	Vaccination 1	1-Month Post-Vaccination 1 Blood Draw	Safety Telephone Contact 1	Vaccination 2	1-Month Post-Vaccination 2 Blood Draw	12-Month Antibody Persistence Visit	24-Month Antibody Persistence Visit
Approximate Month	0	1	6	12	13	24	36
Visit Window	Day 1	28 to 42 Days After Visit 1	168 to 196 Days After Visit 1	336 to 394 Days After Visit 1	28 to 42 Days After Visit 4	336 to 394 Days After Visit 4	700 to 756 Days After Visit 4
Informed consent	X						
Review eligibility criteria	X						
Demography	X						
Confirm continued eligibility b		X	X	X	X	X	X
Medical history	X						
Physical examination	X			X			
Record previous PRP-OMP vaccinations	X						
Urine pregnancy test for female participants (obtain results prior to vaccination)	X			X			
Oral temperature (prior to vaccination)	X			X			

Group 1 (0- and 12-Month Schedule)							
Visit Identifier	Visit 1	Visit 2	Visit 3	Visit 4	Visit 5	Visit 6	Visit 7 a
Visit Description	Vaccination 1	1-Month Post-Vaccination 1 Blood Draw	Safety Telephone Contact 1	Vaccination 2	1-Month Post-Vaccination 2 Blood Draw	12-Month Antibody Persistence Visit	24-Month Antibody Persistence Visit
Approximate Month	0	1	6	12	13	24	36
Visit Window	Day 1	28 to 42 Days After Visit 1	168 to 196 Days After Visit 1	336 to 394 Days After Visit 1	28 to 42 Days After Visit 4	336 to 394 Days After Visit 4	700 to 756 Days After Visit 4
Randomization	X						
Obtain blood sample (~25 mL)	X	X			X	X	X
Study intervention administration and observation c	X			X			
Record nonstudy vaccinations d		X	X	X	X	X	
Provide the participant with a contact card	X						
Provide the participant with a memory aid		X			X		
Complete Study Visit/Telephone Contact AE Checklist e		X	X	X	X	X	X
Record concomitant medications used to treat AEs	X	X	X	X	X	X	X

Group 1 (0- and 12-Month Schedule)							
Visit Identifier	Visit 1	Visit 2	Visit 3	Visit 4	Visit 5	Visit 6	Visit 7 a
Visit Description	Vaccination 1	1-Month Post-Vaccination 1 Blood Draw	Safety Telephone Contact 1	Vaccination 2	1-Month Post-Vaccination 2 Blood Draw	12-Month Antibody Persistence Visit	24-Month Antibody Persistence Visit
Approximate Month	0	1	6	12	13	24	36
Visit Window	Day 1	28 to 42 Days After Visit 1	168 to 196 Days After Visit 1	336 to 394 Days After Visit 1	28 to 42 Days After Visit 4	336 to 394 Days After Visit 4	700 to 756 Days After Visit 4
(S)AE collection appropriate for the visit f	X	X	X	X	X	X	X

Abbreviations: MAE = medically attended adverse event; NDCMC = newly diagnosed chronic medical condition; PRP-OMP = polyribosyribitol phosphate oligosaccharide of *Haemophilus influenzae* type b conjugated to outer membrane protein.

Note: A safety follow-up telephone contact should occur for all participants who withdraw from the study within 6 months after any vaccination. Refer to Section 8.1.1.3 in the protocol.

- Visits 8, 9, and 10 will not be conducted for participants in Group 1.
- Ensure that the participant continues to be eligible for the study and continues to comply with contraception requirements, as appropriate.
- Observe the participant for at least 30 minutes (or longer as per local practice) after the study intervention administration for any acute reactions.
- Record nonstudy vaccinations as described in Section 6.5 in the protocol.
- Checklist includes questions regarding NDCMCs, MAEs, and missed days of school or work, as well as neuroinflammatory and autoimmune conditions, such as transverse myelitis, uveitis, optic neuritis, and multiple sclerosis.
- Please refer to Section 8.3.1 in the protocol.

Group 2 (0- and 36-Month Schedule)								
Visit Identifier	Visit 1	Visit 2	Visit 3	Visit 4	Visit 5 a	Visit 8	Visit 9	Visit 10
Visit Description	Vaccination 1	1-Month Post-Vaccination 1 Blood Draw	Safety Telephone Contact 1	Vaccination 2	1-Month Post-Vaccination 2 Blood Draw	Safety Telephone Contact 2	Vaccination 3	1-Month Post-Vaccination 3 Blood Draw
Approximate Month	0	1	6	12	13	24	36	37
Visit Window	Day 1	28 to 42 Days After Visit 1	168 to 196 Days After Visit 1	336 to 394 Days After Visit 1	28 to 42 Days After Visit 4	336 to 394 Days After Visit 4	700 to 756 Days After Visit 4	28 to 42 Days After Visit 9
Informed consent	X							
Review eligibility criteria	X							
Demography	X							
Confirm continued eligibility b		X	X	X	X	X	X	X
Medical history	X							
Physical examination	X			X			X	
Record previous PRP-OMP vaccinations	X							
Urine pregnancy test for female participants (obtain results prior to vaccination)	X			X			X	
Oral temperature (prior to vaccination)	X			X			X	
Randomization	X							
Obtain blood sample (~25 mL)	X	X			X			X
Study intervention administration and observation c	X			X			X	
Record nonstudy vaccinations d		X	X	X	X	X	X	X

Group 2 (0- and 36-Month Schedule)									
Visit Identifier	Visit 1	Visit 2	Visit 3	Visit 4	Visit 5 a	Visit 8	Visit 9	Visit 10	
Visit Description	Vaccination 1	1-Month Post-Vaccination 1 Blood Draw	Safety Telephone Contact 1	Vaccination 2	1-Month Post-Vaccination 2 Blood Draw	Safety Telephone Contact 2	Vaccination 3	1-Month Post-Vaccination 3 Blood Draw	
Approximate Month	0	1	6	12	13	24	36	37	
Visit Window	Day 1	28 to 42 Days After Visit 1	168 to 196 Days After Visit 1	336 to 394 Days After Visit 1	28 to 42 Days After Visit 4	336 to 394 Days After Visit 4	700 to 756 Days After Visit 4	28 to 42 Days After Visit 9	
Provide the participant with a contact card	X								
Provide the participant with a memory aid		X			X				
Complete Study Visit/Telephone Contact AE Checklist e		X	X	X	X	X	X	X	
Record concomitant medications used to treat AEs	X	X	X	X	X	X	X	X	
(S)AE collection appropriate for the visit f	X	X	X	X	X	X	X	X	

Abbreviations: MAE = medically attended adverse event; NDCMC = newly diagnosed chronic medical condition; PRP-OMP = polyribosyribitol phosphate oligosaccharide of *Haemophilus influenzae* type b conjugated to outer membrane protein.

Note: A safety follow-up telephone contact should occur for all participants who withdraw from the study within 6 months after any vaccination. Refer to Section 8.1.1.3 in the protocol.

- Visits 6 and 7 will not be conducted for participants in Group 2.
- Ensure that the participant continues to be eligible for the study and continues to comply with contraception requirements, as appropriate.
- Observe the participant for at least 30 minutes (or longer as per local practice) after the study intervention administration for any acute reactions.
- Record nonstudy vaccinations as described in Section 6.5 in the protocol.
- Checklist includes questions regarding NDCMCs, MAEs, and missed days of school or work, as well as neuroinflammatory and autoimmune conditions, such as transverse myelitis, uveitis, optic neuritis, and multiple sclerosis.
- Please refer to Section 8.3.1 in the protocol.

### **3. ENDPOINTS AND BASELINE VARIABLES: DEFINITIONS AND CONVENTIONS**

[Appendix 1](#) shows how the study estimands and endpoints relate to each objective.

#### **3.1. Primary Endpoints**

##### **3.1.1. Primary Immunogenicity Endpoints**

- hSBA titer for each of the primary MenB test strains (A22, A56, B24, and B44).

##### **3.1.2. Primary Safety Endpoints**

- AEs, SAEs, MAEs, NDCMCs, and immediate AEs.
- Days missing from school or work because of AEs.

#### **3.2. Secondary Endpoints**

##### **3.2.1. Secondary Immunogenicity Endpoints**

- hSBA titer for each of the MenACWY test strains.
- hSBA titer for each of the primary MenB test strains (A22, A56, B24, and B44).

#### **3.3. Exploratory Endpoints**

- hSBA titer for each of the MenACWY test strains.
- hSBA titer for each of the primary MenB test strains (A22, A56, B24, and B44).

hSBA titers assessed for either MenB or MenACWY will be analyzed as below:

hSBA titers  $\geq$  LLOQ will be derived as follows:

- = •, if the assay result is missing, indeterminate, or otherwise unavailable;
- = 1, if the assay result meets the specific LLOQ value;
- = 0, if the assay result does not meet the specific LLOQ value.

Similarly, for all hSBA titers assessed, binary variables of assay results at each visit where assay titers are analyzed, and that achieve specific thresholds, will be derived as follows:

- = •, if the assay result is missing, indeterminate, or otherwise unavailable;
- = 1, if the assay result meets the specific threshold value;
- = 0, if the assay result does not meet the specific threshold value.

The threshold values for MenB hSBA titers are:

- $\geq 1:4, \geq 1:8, \geq 1:16, \geq 1:32, \geq 1:64$ , and  $\geq 1:128$

For the exploratory objective to further describe the immune response for MenB induced by 2 doses of MenABCWY administered on both dose schedules, the endpoints related to the percentage of participants with hSBA titers  $\geq 1:8, \geq 1:16, \geq 1:32, \geq 1:64$ , and  $\geq 1:128$  may not be reported. This will not extend to reporting of the primary endpoint of percentage of participants achieving hSBA titers  $\geq$  LLOQ and  $\geq 1:4$ .

A composite response will be computed at Visit 5 (1 month after the second dose of MenABCWY in Group 1) and Visit 10 (1 month after the second dose of MenABCWY in Group 2). The composite response is defined as participants who have assay results that are  $\geq$  LLOQ for all 4 of the primary MenB strains at the same visit. The composite response will be computed as follows:

- = •, if the assay result is missing, indeterminate, or otherwise unavailable for at least 1 of the 4 MenB primary strains;
- = 1, if all 4 MenB primary strains have assay results  $\geq$  LLOQ at the same visit;
- = 0, if not all 4 MenB primary strains have assay results  $\geq$  LLOQ.

The 4-fold response in assay titers from baseline (Visit 1, before vaccination) to 1 month after Vaccination 1 (Visit 2) and 1 month after the second dose of MenABCWY (Visit 5 for Group 1 and Visit 10 for Group 2) will be defined as follows:

- For participants with a baseline hSBA titer below the LOD (or an hSBA titer of  $<1:4$ ), a 4-fold response is defined as an hSBA titer of  $\geq 1:16$ .
- For participants with a baseline hSBA titer of  $\geq$  LOD (ie, hSBA titer of  $\geq 1:4$ ) and  $<$  LLOQ (ie, hSBA titer of 1:8), a 4-fold response is defined as an hSBA titer of  $\geq 4$  times the LLOQ.
- For participants with a baseline hSBA titer of  $\geq$  LLOQ, a 4-fold response is defined as an hSBA titer of  $\geq 4$  times the baseline titer.

The 4-fold response variable for the MenB and MenACWY strains will be computed as follows:

- = •, if the assay result at baseline or specific time point is missing, indeterminate, or otherwise unavailable;
- = 1, if the assay result meets 1 of the 3 definitions for a 4-fold response;
- = 0, if the assay result does not meet 1 of the 3 definitions for a 4-fold response.

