## 2.1.4. Primary Estimands

- **Primary Immunogenicity Estimands**

For the first objective (to describe the immune response for MenB induced by 2 doses of MenABCWY administered on a 0- and 12-month schedule), the primary estimand has the following attributes:

- Population: Participants receiving 2 doses of MenABCWY and who are in compliance with the key protocol criteria (evaluable participants).
- Variable: hSBA titer for each of the primary MenB test strains (A22, A56, B24, and B44).
- Intercurrent event(s): Participants will be summarized according to the vaccine group to which they were randomized. Missing serology data will not be imputed.
- Population-level summary: The percentage of participants achieving an hSBA titer  $\geq$  LLOQ (1:16 for strain A22 and 1:8 for strains A56, B24, and B44) for each of the 4 primary MenB test strains at baseline and 1 month after the second dose of MenABCWY in Group 1 (0- and 12-month schedule).

For the second objective (to describe the immune response for MenB induced by 2 doses of MenABCWY administered on a 0- and 36-month schedule), the primary estimand has the following attributes:

- Population: Participants receiving 2 doses of MenABCWY and who are in compliance with the key protocol criteria (evaluable participants).
- Variable: hSBA titer for each of the primary MenB test strains (A22, A56, B24, and B44).
- Intercurrent event(s): Participants will be summarized according to the vaccine group to which they were randomized. Missing serology data will not be imputed.
- Population-level summary: The percentage of participants achieving an hSBA titer  $\geq$  LLOQ (1:16 for strain A22 and 1:8 for strains A56, B24, and B44) for each of the 4 primary MenB test strains at baseline and 1 month after the second dose of MenABCWY in Group 2 (0- and 36-month schedule).

The planned analyses for the primary endpoints as related to the estimands are outlined in [Section 6.1](#).

- **Primary Safety Estimands**

For the primary safety objective to describe the safety profile of MenABCWY when administered on a 0- and 12-month and 0- and 36-month schedule as measured by AEs, SAEs, MAEs, NDCMCs, and immediate AEs, the estimand has the following attributes:

- Population: Participants receiving at least 1 dose of study intervention.
- Variable: AEs, SAEs, MAEs, NDCMCs, and immediate AEs.

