###### **5.2.1.1. Immunogenicity Data**

Each MenB ([Table 7](#)) and MenACWY ([Table 8](#)) strain has a validated LLOQ value defined.

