**Table 7. Validated hSBA LOD and LLOQ for MenB Primary Strains**

Strain Type	Strain Variant	LOD	LLOQ
Primary	A22	1:4	1:16
	A56	1:4	1:8
	B24	1:4	1:8
	B44	1:4	1:8

Abbreviations: hSBA = serum bactericidal assay using human complement; LLOQ = lower limit of quantitation; LOD = limit of detection; MenB = *Neisseria meningitidis* group B.

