### **6.3. Exploratory Endpoints**

#### **6.3.1. Exploratory Immunogenicity Endpoints**

##### **6.3.1.1. hSBA Titer for Each of the Primary MenB Test Strains (A22, A56, B24, and B44)**

###### **6.3.1.1.1. Main Analysis**

- Estimand strategy: Hypothetical.
- Analysis set: Post-Vaccination 2 evaluable populations for Groups 1 and 2.
- Analysis methodology: Exact 2-sided 95% CIs for the percentages using the Clopper-Pearson method.

- Intercurrent events and missing data: Missing serology results will not be imputed. Participants will be summarized according to the vaccine group to which they were randomized.
- The percentage of participants with hSBA titers  $\geq 1:4$ ,  $\geq 1:8$ ,  $\geq 1:16$ ,  $\geq 1:32$ ,  $\geq 1:64$ , and  $\geq 1:128$  for each of the 4 primary MenB test strains at baseline and 1 month after the second dose of MenABCWY for each group, separately. The percentage of participants with hSBA titers  $\geq 1:8$ ,  $\geq 1:16$ ,  $\geq 1:32$ ,  $\geq 1:64$ , and  $\geq 1:128$  may not be reported out.
- MenB hSBA GMTs for each of the 4 primary MenB test strains at baseline and 1 month after the second dose of MenABCWY for Groups 1 and 2, separately.
- The percentage of participants achieving an hSBA titer  $\geq$  LLOQ (1:16 for A22 and 1:8 for A56, B24, and B44) for all primary MenB test strains combined (composite response) at baseline and 1 month after the second dose of MenABCWY for each group, separately.
- The percentage of participants achieving an hSBA titer  $\geq$  LLOQ for each of the 4 primary MenB test strains at 13 months after the first dose of MenABCWY in Group 2.
- The percentage of participants achieving at least a 4-fold rise in hSBA titer from baseline for each of the 4 primary MenB test strains at 1 month after the second dose of MenABCWY for each group, separately.
  - For participants with a baseline hSBA titer below the LOD (or an hSBA titer of  $< 1:4$ ), a 4-fold response is defined as an hSBA titer of  $\geq 1:16$ .
  - For participants with a baseline hSBA titer of  $\geq$  LOD (ie, hSBA titer of  $\geq 1:4$ ) and  $<$  LLOQ, a 4-fold response is defined as an hSBA titer of  $\geq 4$  times the LLOQ.
  - For participants with a baseline hSBA titer of  $\geq$  LLOQ, a 4-fold response is defined as an hSBA titer of  $\geq 4$  times the baseline titer.

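### SAP 3.3's shared 4-fold-response rule gives the LLOQ as 1:8, but strain A22's LLOQ is 1:16, so A22 responders could be miscounted

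*SAP*

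**What the plan says.** SAP Section 3.3 defines the 4-fold response in three branches, according to the baseline titer:

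1. Baseline below the LOD (1:4): response is a post-dose titer of at least 1:16.
2. Baseline from the LOD up to the LLOQ: response is at least four times the LLOQ. This branch is worded "LLOQ (ie, hSBA titer of 1:8), a 4-fold response is defined as an hSBA titer of" that multiple.
3. Baseline at or above the LLOQ: response is at least four times the baseline.

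The section then fixes the coding for all strains together: "The 4-fold response variable for the MenB and MenACWY strains will be computed as follows". The value is 0 "if the assay result does not meet 1 of the 3 definitions for a 4-fold response".

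Elsewhere the LLOQ is strain-specific. SAP 5.2.1.1 says that each MenB and MenACWY "strain has a validated LLOQ value defined". SAP 2.1.4 gives the MenB values as "1:16 for strain A22 and 1:8 for strains A56, B24, and B44", and Table 7 ("Validated hSBA LOD and LLOQ for MenB Primary Strains") agrees, with an LOD of 1:4 for all four strains. Table 8 gives 1:8 for all four ACWY serogroups.

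The MenB main analysis in SAP 6.3.1.1.1 states the second branch without the parenthesis: "LLOQ, a 4-fold response is defined as an hSBA titer of" four times the LLOQ or more.

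**The concern.** The parenthesis in Section 3.3 gives a single numerical LLOQ to a rule that expressly covers A22, and that number is wrong for A22. The pattern of use suggests where it came from. All eight MenB-specific statements of the rule omit it: SAP 2.1.6 (both groups), 6.3.1.1.1 and Appendix 1 (both groups), and protocol Section 3 (both groups) and 9.4.1. Outside Section 3.3 it appears only in ACWY text (SAP 6.3.1.2.1 and 6.3.1.3.1, and the two ACWY lists in protocol 9.4.1), where 1:8 is correct. It looks like ACWY wording carried into a shared definition.

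Section 3.3 is where the 1/0/missing coding of this variable is set, so a programmer could reasonably work from it. Two results would be affected: the exploratory A22 4-fold rate in each group, and the Group 2 comparison of that rate's lower 95% limit with 75% (SAP 6.3.1.1.2 and Table 9).

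**Working it through.** **Inputs.** LOD 1:4 and A22 LLOQ 1:16 (SAP Table 7); the three branches and the 0 coding (SAP 3.3); 75% for A22 (SAP Table 9); Clopper-Pearson 95% intervals (SAP 5.2.1); 150 per group with up to 20% excluded (protocol 9.2), so 150 × 0.80 = 120 evaluable. Assumption: titers occur in two-fold steps. The documents list two-fold thresholds but do not say that reported titers are limited to them.

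**Step 1: how the parenthesis can be read for A22.**

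- Reading A: LLOQ is 1:8 in branches 2 and 3.
- Reading B: 1:8 only caps the baseline range of branch 2; the multiplier and branch 3 use 1:16.
- Reading C: 1:8 is both the cap and the multiplier in branch 2; branch 3 uses 1:16.
- Reading D: the parenthesis describes the baseline itself, so branch 2 covers only a baseline of 1:8; the multiplier and branch 3 use 1:16.

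Minimum A22 post-dose titer that counts as a response:

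| Baseline | LLOQ 1:16 (Table 7) | A | B | C | D |
|---|---|---|---|---|---|
| <1:4 | 1:16 | 1:16 | 1:16 | 1:16 | 1:16 |
| 1:4 | 1:64 | 1:32 | 1:64 | 1:32 | none |
| 1:8 | 1:64 | 1:32 | none | none | 1:64 |
| 1:16 | 1:64 | 1:64 | 1:64 | 1:64 | 1:64 |
| 1:32 | 1:128 | 1:128 | 1:128 | 1:128 | 1:128 |

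With the Table 7 value, baselines of 1:4 and 1:8 are both in branch 2 and need 4 × 16 = 64. Under A, a baseline of 1:4 needs 4 × 8 = 32 (branch 2), and a baseline of 1:8 needs 4 × 8 = 32 (branch 3). Under B and C, a baseline of 1:8 is neither below 1:8 nor at or above 1:16. It meets no definition and is coded 0 at any post-dose titer. Under D the same happens to a baseline of 1:4.

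**Step 2: who is misclassified.** Take 8 baselines (<1:4 to 1:256) by 11 post-dose titers (up to 1:2048), 88 cells, and compare each reading with LLOQ 1:16.

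- A: 2 cells differ, both over-counts (baseline 1:4 or 1:8, post-dose 1:32).
- B: 6 cells differ, all under-counts (baseline 1:8, post-dose 1:64 to 1:2048).
- C: 7 cells differ, 1 over-count (1:4 to 1:32) and the same 6 under-counts as B.
- D: 6 cells differ, all under-counts (baseline 1:4, post-dose 1:64 to 1:2048).

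**Step 3: effect on the 75% comparison.** The Clopper-Pearson lower limit for x responders of n is the 2.5th percentile of Beta(x, n − x + 1). As a check on the method, Clopper-Pearson half-widths at n = 120 for 60, 70, 80 and 90% are 9.09, 8.53, 7.51 and 5.77. These reproduce protocol Table 4 (9.1, 8.5, 7.5, 5.8).

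One participant is 1/120 = 0.83 percentage points. The lower limits on either side of 75% are:

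| n | Responders | Lower limit | Responders | Lower limit |
|---|---|---|---|---|
| 110 (illustrative) | 91 | 74.35% | 92 | 75.38% |
| 120 (planned) | 99 | 74.50% | 100 | 75.44% |
| 130 (illustrative) | 107 | 74.65% | 108 | 75.51% |

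At n = 120 a single over-count matters for the 75% value only if the true count is 99, and a single under-count only if it is 100. More misclassifications widen that range. The documents give no A22 baseline or post-dose titer distribution, so the number misclassified cannot be calculated.

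**The case against.** The best reply is that the SAP as a whole already settles the matter. The operative words of the rule are multiples of the LLOQ, SAP 5.2.1.1 and Table 7 make the LLOQ strain-specific, and the MenB analysis section carries no 1:8. Section 3.3 itself derives the threshold variable as 1 "if the assay result meets the specific LLOQ value". On this view the rule is the same throughout, with one stray illustrative value, and any competent programmer would use 1:16. Readings B, C and D are also strained: B and C give the LLOQ two values within one rule, B and C call a participant who goes from 1:8 to 1:2048 a non-responder, and D does the same for one who goes from 1:4 to 1:2048.

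Much of this stands. The strain-specific reading is almost certainly what was meant, and A is the most natural literal misreading. It also follows that a miscount is possible, not established. But Section 3.3 is an operative derivation that names the MenB strains, and the SAP does not say that 6.3.1.1.1 takes precedence. The SAP introduction says the programming rules are prepared separately from the methods in the SAP. Those rules are not available here, so which wording the program follows is unknown.

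**Conclusion.** The concern holds. For A22, the LLOQ printed in SAP 3.3 contradicts SAP 2.1.4 and Table 7, and following Section 3.3 literally codes some participants differently from 6.3.1.1.1. The direction depends on the reading: over-count under A, under-count under B or D, both under C. The net size is unknown and may be zero.

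The reach is narrow. Only A22 baselines of 1:4 or 1:8 are involved, and only the 4-fold-rise endpoint. The primary endpoint (titer at or above the LLOQ), the composite response, and the other three MenB strains and four ACWY serogroups are unaffected. The Table 9 comparison carries no hypothesis test and its thresholds are reference values, so no formal decision depends on it. The point is minor. The cell counts rest on two-fold titer steps, and the switch point of 99/100 rests on 120 evaluable participants.

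**What to change.** In SAP 3.3, delete the parenthesis in the second branch, or replace it with a reference to the strain-specific LLOQ in Tables 7 and 8 (1:16 for A22; 1:8 for all other strains). Then confirm in the programming rules and code that A22 uses 1:16 wherever the LLOQ enters, which is branches 2 and 3 only. Baselines of 1:4 and 1:8 should both fall in branch 2 and require a post-dose titer of at least 1:64. The cost is one line of SAP text and one programming check. No data collection, sample size or other analysis changes.
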